#### **Primary Patency:**

- Time from PhotoFix implantation to the time when patency in the vessel is documented as lost
  - Loss of patency includes loss of previously palpable pulses, presentation of recurrent symptoms, a drop in ABI $>0.15$  in the case of lower limb artery repair, Doppler ultrasound findings of occlusion, angiography of the affected vessel or a combination of these.

Loss of patency will also be considered if an intervention to restore or maintain patency is documented. In the event that loss of patency is documented as “no” on the Follow-up eCRFs and evidence of an intervention involving patency restoration is reported on the Adverse Event eCRF, a query will be issued and resolved appropriately.

### 2.9.2 Secondary Analysis

- **Overall Survival:**

- Percent of patients surviving
  - *Early mortality:* Death  $< 30$  days following PhotoFix implantation
  - *Late mortality:* Death  $\geq 30$  days following PhotoFix implantation

- **All-Cause Reoperation Rate:**

- Percent of patients requiring reoperations
  - Reoperation includes the repair or alteration of the surgical area around the patch.

- **Device-Related Reoperation Rate:**
  - Percent of patients requiring unplanned reoperations that are documented as possibly, probably or definitely, device-related
- **Explant Rate:**
  - Percent of patients requiring device explants
    - Explants will include the removal of PhotoFix for any reason after implantation.
- **Adverse Event Rate:**
  - Percent of patients who experienced at least one adverse event
  - Percent of patients who experienced at least one device-related adverse event
- **Restenosis Rate:**
  - Percent of patients who develop stenosis
    - Stenosis is considered as the recurrence of abnormal narrowing of an artery or vein after corrective surgery.
    - Categorization of stenosis  $\geq 50\%$  will occur if data is available.
- (Hemodialysis Access Repair only)  
**Secondary Patency:**
  - Time from implantation to the point where the access is abandoned.

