6.1 Study Endpoints & Variables

In the case of CEAs, the primary endpoint of the study will be rate of ipsilateral central neurologic events.

- Ipsilateral central neurologic events: Transient ischemic attack, amaurosis fugax, stroke, and symptomatic carotid occlusion.

In the case of all other (non-CEA) vascular procedures, the primary endpoint of the study will be primary patency in the target artery or vein.

- Primary patency (of target vessel): Loss of patency will be determined by the loss of previously palpable pulses, patients presenting with recurrent symptoms, a drop in ABI >0.15 in the case of lower limb artery repair, Doppler ultrasound findings of occlusion, angiography of the affected vessel or a combination of these.

The secondary endpoints of the study will include: overall survival rate, all-cause reoperation rate, device-related reoperation rate, explant rate, restenosis rate, adverse event rate, and secondary patency (HAR only).

- Overall Survival:
 - Early mortality: Death < 30 days following PhotoFix implantation.
 - Late mortality: Death ≥ 30 days following PhotoFix implantation, until last day of follow-up.
- All-Cause Reoperation Rate: The total number of reoperations required in patients over the follow-up period, which include the repair or alteration of the surgical area around the patch.

- **Device-Related Reoperation Rate:** The total number of unplanned reoperations required in patients over the follow-up period, which are determined by the surgeon to be device-related.
- **Explant Rate:** The total number of device explants over the course of follow-up. Explants will include the removal of PhotoFix for any reason after implantation.
- **Restenosis Rate:** The total number of documented cases of stenosis documented as the recurrence of abnormal narrowing of a vessel after corrective surgery.
- **Adverse Event Rate:** The total number of any unfavorable and unintended sign (including an abnormal laboratory finding), symptom, or disease temporarily associated with the use of a device, whether or not related to the device.
- **Secondary Patency (HAR only):** The time from implantation to the point where the access is abandoned.

Statistical analysis will be used to assess all study endpoints as applicable.

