6.7 Statistical Analysis Plan

Enrolled patients will be described in aggregate and by indication (as deemed appropriate); baseline characteristics will include, but not limited to, age, sex, race, ethnicity, body mass index (BMI), comorbidities, fundamental diagnosis/etiology, and pertinent surgical history. Operative details will be described in aggregate and include a summary of the types of procedures performed, by relevant category. Parameters with continuous data types will be summarized using descriptive statistics, i.e., mean, standard deviation, and range. Categorical clinical parameters will be summarized based on percentages.

Ipsilateral central neurologic event rate, overall survival, re-operation rate, explant rate, and restenosis rate ($\geq 50\%$ stenosis) will be summarized based on percentages of affected patients and included in a table, which will summarize the endpoints in aggregate and by surgical indication (ex. CAS, ESRD, PAD, AAA, etc.). The summary of ipsilateral central neurologic event rates will include all events (transient ischemic attack, amaurosis fugax, stroke, and symptomatic carotid occlusion), as well as the incidence of each event individually.

Additional analysis of follow-up data will also be performed with the Kaplan-Meier method, as deemed appropriate by the incidence of events. Kaplan-Meier plots may be generated for endpoints including overall survival, primary patency, secondary patency, as well as freedom from ipsilateral central neurologic event rate, re-operation, explant, and restenosis ($\geq 50\%$ stenosis). Kaplan-Meier plots for survival will include the following mortality classifications: all causes of mortality, vascular-related mortality and device-related mortality (as applicable). The remaining plots will be specific to indication, if the sample sizes allow for the creation of meaningful plots.

The incidence of adverse events will be categorized and summarized with percentages for the aggregate sample. Adverse events will be divided into early and late post-operative events to represent the distribution of occurrences. Events will be considered as early events if the event occurs <30 days after the operation, while late post-operative events will be considered to be all events happening after this time period. Early and late events will be presented by indication for surgery, seriousness of event, and relation to PhotoFix. Adverse events occurring secondary to

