9. Perioperative or Post-Operative Adverse Events *If yes, fill out the Adverse Event eCRF.	 Yes  No
If yes, timing of event	 Peri-Operative  Post-Operative
10. Length of Implanted Patch (cm)	 Unknown
11. Width of Implanted Patch (cm)	 Unknown

Follow-Up eCRF	
Study Subject ID	
1. Date of Visit	/ / Month/Day/Year
2. Indicate Visit Number *If Visit 5, fill out End of Study eCRF.	 Visit 3, 1 month post-op  Visit 4, 3 months post-op  Visit 5, 6 months post-op  Unscheduled Visit
3. Indicate Current Subject Status *If withdrawn, fill out End of Study eCRF.	 Active  Withdrawn
4. Were there any post-operative Adverse Events since last study visit? *If yes, fill out the Adverse Event eCRF.	 Yes  No
5. Was patency lost in the target artery/vein since the last study visit? *If yes, fill out the Adverse Event eCRF.	 Yes  No
If yes, indicate the number of instances that patency was lost	
If yes, indicate date(s) patency was lost	/ / (most recent) Month/Day/Year / /  N/A Month/Day/Year / /  N/A Month/Day/Year
If yes, indicate reason(s) patency was lost	 Aneurysm  Infection  Restenosis  Thrombosis  Other: _____ *Select all that apply
If yes, was a surgical (open or endovascular) procedure performed to re-establish patency?	 Yes  No  Unknown
If yes, was any loss of patency PhotoFix-related?	 Definitely  Probably  Possibly  Unrelated
If yes, was patency successfully re-established for the most recent event?	 Yes  No  Unknown
6. Did the patient undergo any vascular	 Yes

Follow-Up eCRF	

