surgery (open or endovascular) since the last study visit? *If yes, fill out the Adverse Event eCRF.	 No  Unknown
If yes, date surgery occurred	/ / Month/Day/Year
If yes, indication for surgery?	 Infection  Re-establish Hemodialysis Access Patency  Rupture  Stenosis  Thrombosis  Other: _____ *Select all that apply
If yes, describe the surgical procedure	
If yes, did the surgery involve PhotoFix or the surrounding patch area?	 Yes  No
If yes, was PhotoFix explanted? *If Partially or Completely, fill out Explant eCRF	 No  Partially  Completely
If yes, was the need for surgery related to PhotoFix?	 Definitely  Probably  Possibly  Unrelated
7. Has there been evidence of restenosis since the last study visit?	 Yes  No  Unknown
If yes, was an imaging evaluation performed *If yes, complete the Imaging Evaluation eCRF	 Yes  No  Unknown
If yes, indicate the degree of restenosis.	 Unknown
8. Describe any other significant events which have occurred since the last follow-up visit.	 None

Adverse Event eCRF	
Study Subject ID	
1. Date Adverse Event Reported	____ / ____ / ____ Month/Day/Year
2. Is this an update to a previously reported event?	 Yes  No
3. Start Date	____ / ____ / ____ Month/Day/Year
4. Stop Date	____ / ____ / ____ Month/Day/Year

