## **2.18. Secondary Patency**

A Kaplan-Meier (KM) survival curve for secondary patency will be estimated for enrolled patients who received PhotoFix for hemodialysis access repair (HAR).

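### Secondary patency is time to access abandonment, but no case report form asks whether or when the access was abandoned, and neither document defines the term

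*SAP*

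**What the plan says.** Both documents give this endpoint the same event, for HAR only. SAP 2.9.2 has "Time from implantation to the point where the access is abandoned", and Protocol 6.1 has "The time from implantation to the point where the access is abandoned". SAP 2.18 is a single sentence: a Kaplan-Meier "survival curve for secondary patency will be estimated for enrolled patients who received PhotoFix for hemodialysis access repair (HAR"). It names no form field and no event date.

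Protocol 6.3 points to Appendix D for the variables to be obtained. The post-operative items that come closest are all on the Follow-Up eCRF:

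- Item 5 asks "Was patency lost in the target artery/vein since the last study visit" (Yes or No). A Yes opens up to three dates of loss, the reasons, whether a procedure was done to restore patency, and "was patency successfully re-established for the most recent event" (Yes, No or Unknown).
- Item 6 covers any vascular surgery since the last visit (Yes, No or Unknown), with its date. One listed indication is "Re-establish Hemodialysis Access Patency", and there is a free-text line, "If yes, describe the surgical procedure".
- Item 8 is open text for other significant events and has no date field.

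Nothing on these items, or on the Adverse Event, Explant or End of Study forms, mentions abandonment. Appendix E does not define it.

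**The concern.** Under the stated definition, an access that loses patency and is then reopened has not had the event; it stays event-free until it is given up. That is what separates secondary from primary patency. The forms date the loss and the operation, but not the giving up.

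The contrast with primary patency is plain. SAP 2.9.1 lists criteria for that endpoint and provides for a query when the Follow-Up and Adverse Event forms disagree. Secondary patency has neither a criterion nor a source.

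Whoever builds the curve would therefore decide, with the data in hand, which entries count as abandonment and which date to use. Two analysts could draw different curves from the same database, and a curve labelled secondary patency could in part be dating patency loss or surgery.

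**Working it through.** The plan gives no HAR count and no expected abandonment rate, so there is no figure of its own to reproduce. The check sets the forms against the definition and then sizes an error.

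**Step 1. Where abandonment could appear, and what date would come with it (Protocol Appendix D).**

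| Field | Asks about abandonment? | Date attached |
|---|---|---|
| Follow-Up item 5, patency not re-established | No; asks about patency | Most recent loss |
| Follow-Up item 5, reason Other | No | Loss of patency |
| Follow-Up item 6, indication Other or procedure text | No | Surgery |
| Follow-Up item 8, free text | No | None; bounded by two visits |
| Adverse Event, category Other or narrative | No | Event start |
| Explant, reason Other or procedure text | No | Explant |
| End of Study, reason Other or details | No | Discontinuation |

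No row carries an abandonment date. The one dialysis-specific indication in item 6 describes an operation to keep the access working, which is the opposite of abandoning it.

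**Step 2. The structured proxy.** Item 5 can be read as a chain: patency lost, not re-established, dated at the latest loss. In a patient with one loss and no earlier intervention, that date is also the primary patency event date, so both curves step down together. The chain misses an access given up with no recorded loss, and an Unknown could go either way.

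**Step 3. Precision if only item 8 holds the event.** Assume months 1, 3 and 6 are days 30, 90 and 180. The visit window is 14 days either side (Protocol 3.2). The interval within which the event is known to lie is then:

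- surgery to 1-month visit: 30 − 14 = 16 to 30 + 14 = 44 days;
- 1- to 3-month visit: (90 − 14) − (30 + 14) = 32 to (90 + 14) − (30 − 14) = 88 days;
- 3- to 6-month visit: (180 − 14) − (90 + 14) = 62 to (180 + 14) − (90 − 14) = 118 days.

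**Step 4. Effect on the 6-month estimate.** Assume complete follow-up, with n HAR patients and d abandonments. The Kaplan-Meier estimate at 6 months is 1 − d/n, so one patient wrongly counted or wrongly missed moves it by 100/n points:

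- n = 10: 100/10 = 10.0 points;
- n = 20: 100/20 = 5.0 points;
- n = 30: 100/30 = 3.3 points.

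Under the same assumption, a wrong date that stays inside the 6 months shifts the step on the curve but not the 6-month value. Misclassification is what changes the headline number; misdating changes the shape.

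**The case against.** The strongest case on the other side is that existing safeguards narrow the gap. A Yes to item 5 or item 6 calls for an Adverse Event form, which has a start date, a narrative and a status. Protocol 4.3 asks for source notes on adverse events and 24-hour reporting of vascular complications. Protocol 6.5 lets the data manager request further documentation, and full source verification is intended (Protocol 6.6 and 7). Item 5 also supplies a usable structured proxy.

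All of this stands, and it makes the wholly missed case narrow: an access given up with no recorded patency loss, operation or adverse event. It does not close the gap. Nothing prompts a site to record abandonment, and the SAP does not adopt the proxy.

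Some stronger readings are tempting, but the documents do not support them:

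- *Abandonment cannot be recorded.* It can, in the several free-text and Other fields listed above.
- *The handling of deaths is ambiguous.* Abandonment is the only event defined. A death with the access not abandoned is not that event, so an ordinary Kaplan-Meier analysis would censor it. Counting deaths as events would be a different endpoint, which the text does not suggest.
- *The missing censoring rule is a fault of this endpoint.* The SAP states no such rule for any of its Kaplan-Meier analyses. SAP 2.9 runs analyses to the end of follow-up, and the End of Study form is dated. Censoring belongs in a comment on the SAP as a whole.
- *Protocol and SAP conflict over the curve.* Protocol 6.7 says "Kaplan-Meier plots may be generated for endpoints including overall survival, primary patency, secondary patency", subject to event incidence and sample size, while SAP 2.18 commits to the curve. The SAP is the detailed analysis document, and nothing here turns on the difference.

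**Conclusion.** The point holds, and it is narrow. The endpoint's event is undefined and has no prompted field or date, and the SAP names no substitute. Followed as written, the secondary patency curve would depend on how each site happens to use free text, or on a proxy not labelled as such.

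The consequence is limited to one descriptive secondary endpoint, with no test attached, in one subgroup of a single-arm study. No primary conclusion is affected. The 10.0, 5.0 and 3.3 points per misclassified patient rest on assumed subgroup sizes and complete follow-up. The documents give no basis for saying how many patients would be misclassified. This is worth correcting because the correction is cheap, not because the study depends on it.

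**What to change.** 1. Add three HAR-only items to the Follow-Up eCRF, for scheduled and unscheduled visits: *Access abandoned since last visit? (Yes/No)*, *Date abandoned* and *Reason*. Print the sponsor's own one-line definition of abandonment beside them. Back-fill by query for HAR patients already past a visit.
2. In SAP 2.18, name *Date abandoned* as the event date, and state that an access which lost patency but was not abandoned stays at risk. Leave the censoring date to a single rule covering all Kaplan-Meier analyses in the SAP.
3. If the forms cannot be changed, pre-specify the item 5 proxy (patency not re-established, dated at the most recent loss), supplemented by item 6 and the Adverse Event form. Label the curve a proxy, and show it with Unknown answers counted both ways.

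The cost is three form items and one definition line for HAR patients only, some query work, and a few sentences in the SAP. No visits or tests are added. The fallback in item 3 needs no form change, but it leaves the event date as that of patency loss.

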## **2.10. Incidence of Central Neurologic Events**

Frequency counts and percentages will be presented in a table for enrolled patients who received PhotoFix during carotid endarterectomy (CEA).

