3.2 Study Size & Duration

Patients will be enrolled at approximately 10 sites. The enrollment period will span the time needed to consent approximately 166 patients. The target sample size is 100; projected enrollment considers a screen failure rate of 33% and an early termination rate of 10%. Enrollment is estimated to take a minimum of 8 months from Institutional Review Board (IRB) approval and site activation. Enrollment will begin at the principal investigator's site and in agreement with all central and local IRB requirements. The enrollment period will continue until the Sponsor decides to stop enrollment. The Sponsor will activate additional sites at their discretion.

A singular anatomical region will be selected for patch use. More than one patch can be used within the repair or reconstruction of this target region. However, patients requiring patches at distinct anatomical regions will be excluded. Additionally, patients undergoing concomitant procedures requiring additional prosthetics (e.g. stents) will be excluded. For complex cases, where clarification on these criteria is required, the Sponsor should be contacted prior to obtaining consent.

Patients undergoing a vascular procedure which falls within the indications for use and requires the use of PhotoFix will be screened and consented for the study, pre-operatively.

The study will collect prospective data at 5 time points; data will be collected pre-operatively, intraoperatively/immediately post-operatively, 1 month post-operatively, 3 months post-operatively, and 6 months post-operatively. All study patients will be expected to participate in all study required evaluations. Patients will be expected to come into the office at the 3 follow-up visits, post hospital discharge. For all post-operative visits outside the hospital, a +/- 14 day window is allowed for schedule fluctuations, but visits should ideally remain at the intended intervals. Data will also be collected on any unscheduled events (i.e. reoperation, explants, etc.) which may occur during the study period.

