another complication will be collected, but not included in the calculation of adverse event rates. Adverse events occurring prior to PhotoFix implant will not be reported.

An interim analysis of the data will be performed approximately 6 months after the initiation of enrollment. The sample size will be dependent on enrollment rate; follow-up could range from 0 days to 5 months. This analysis will be used to assess the interim performance and safety of PhotoFix. The analysis of this data will also be used to address the planned enrollment of the study and to determine if any modifications to the study are necessary.

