## **2.2. Study Population**

All consented patients will be included in the basic patient demographics summary; this section will include data collected on the Demographics Electronic Case Report Form (eCRF). All patients who receive PhotoFix as part of their vascular repair or reconstruction surgery will be considered enrolled and included in all additional summaries and analyses.

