#### **Incidence of Central Neurologic Events:**

- Percent of patients who experienced at least one transient ischemic attack
- Percent of patients who experienced at least one case of amaurosis fugax
- Percent of patients who experienced at least one stroke
- Percent of patients who experienced symptomatic carotid occlusion at least once
- Percent of patients who experienced any of the central neurologic events of interest at least once

- (All Non-Carotid Indications)

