## **2.19. Interim Analysis**

There is an interim analysis planned for January of 2019. This analysis will be used to assess the interim performance and safety of PhotoFix. The interim analysis report will focus on the summary statistics of all primary and secondary endpoints. Sample size, frequency, and percentages will be presented for categorical variables. Sample size, arithmetic mean, standard deviation, median, minimum and maximum will be presented for continuous variables. Summaries will be presented in tables. The creation of KM plots and sub-analyses by surgical indication, device relation or timing of event are not planned.

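### The CEA primary endpoint is planned only as a crude percentage that ignores length of follow-up: a small understatement at the final analysis, a material one at the interim

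*SAP*

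**What the plan says.** SAP 2.9.1 defines the CEA primary analysis as a set of percentages, one for each event type and one for the composite: "Percent of patients who experienced any of the central neurologic events of interest at least once". SAP 2.10 adds only the presentation: "Frequency counts and percentages will be presented in a table for enrolled patients who received PhotoFix during carotid endarterectomy (CEA"). Neither section gives a time horizon, a censoring rule or a confidence interval. Under SAP 2.2, all patients who receive the patch "will be considered enrolled and included in all additional summaries and analyses", whatever their length of follow-up. SAP 2.21 on missing data has no rule for incomplete follow-up.

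Protocol 6.7 makes percentages of affected patients the base summary and adds that "Kaplan-Meier plots may be generated for endpoints including overall survival, primary patency, secondary patency, as well as freedom from ipsilateral central neurologic event rate", with reoperation, explant and restenosis completing the list. SAP 2.11 to 2.16 and 2.18 specify a Kaplan-Meier curve for each of the other endpoints on that list. The CEA primary endpoint is the only one left without.

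The plan expects incomplete follow-up. Protocol 3.2 allows for "an early termination rate of 10" per cent, and Protocol 6.7 says that at the interim "follow-up could range from 0 days to 5 months". For the interim, SAP 2.19 states: "The creation of KM plots and sub-analyses by surgical indication, device relation or timing of event are not planned".

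**The concern.** A crude percentage equals the six-month risk only if every patient is observed for six months or until an event. A patient who leaves at one month without an event stays in the denominator as event-free, although five months were never observed. If loss is unrelated to risk, the error runs one way, towards a lower event rate for the device.

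This is a primary safety endpoint. The interim report is where follow-up is shortest, and Protocol 6.7 gives that report three uses: judging performance and safety, reviewing planned enrolment, and deciding whether the study needs changing. A low interim percentage shown without follow-up time could reassure when much of the risk period has not yet been observed.

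**Working it through.** **The plan's own figure.** Protocol 3.2 aims for 100 patients, with 33% screen failure and 10% early termination, and arrives at about 166 consents. 100 / (0.67 × 0.90) = 165.8, which rounds up to 166, so the figure reproduces. It implies 166 × 0.67 = 111 implanted and 111 × 0.90 = 100 completing, that is about 11 patients leaving early if the 10% falls after implant.

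**Inputs.** From the documents: early termination d = 10%; follow-up of 6 months at the final analysis and 0 to 5 months at the interim. Assumed, because the documents do not give them: a six-month risk R = 10%; dropout times uniform over 6 months; interim follow-up uniform over 0 to 5 months; censoring unrelated to risk; and three patterns of event timing.

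**Formulas.** Let F(t) be the cumulative risk by month t.

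- Final crude rate = (1 − d)R + d × mean of F over 0 to 6 months.
- Interim crude rate = mean of F over 0 to 5 months.
- Constant hazard: λ = −ln(0.90)/6 = 0.01756 per month, and the mean of F over 0 to a is 1 − (1 − e^(−aλ))/(aλ).
- Share p of the risk in month 1, the rest spread evenly: F(t) = Rpt up to month 1, then R[p + (1 − p)(t − 1)/5].

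**Constant hazard.** Final: the mean of F over 0 to 6 is 1 − 0.1000/0.10536 = 0.0509, so the crude rate is 0.90 × 0.1000 + 0.10 × 0.0509 = 9.51%. Interim: 1 − 0.08406/0.08780 = 4.26%. The 5-month risk is 1 − 0.90^(5/6) = 8.41%.

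**Half the risk in month 1.** Final: the mean of F over 0 to 6 is R(0.25 + 2.5 + 1.25)/6 = 0.667R, so the crude rate is 9.67%. Interim: R(0.25 + 2.0 + 0.8)/5 = 6.10%. The 5-month risk is R(0.5 + 0.5 × 4/5) = 9.00%.

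**80% of the risk in month 1.** Final: R(0.4 + 4.0 + 0.5)/6 = 0.817R, so the crude rate is 9.82%. Interim: R(0.4 + 3.2 + 0.32)/5 = 7.84%. The 5-month risk is R(0.8 + 0.2 × 4/5) = 9.60%.

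| Event timing | Final crude (true 10%) | Relative shortfall | Interim crude | 5-month risk | Relative shortfall |
|---|---|---|---|---|---|
| Constant hazard | 9.51% | 5% | 4.26% | 8.41% | 49% |
| Half in month 1 | 9.67% | 3% | 6.10% | 9.00% | 32% |
| 80% in month 1 | 9.82% | 2% | 7.84% | 9.60% | 18% |

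In the limiting case where every dropout leaves on day 0, the final crude rate is 0.90 × 10% = 9.0%, a 10% shortfall. The ratios of crude rate to six-month risk are nearly the same at assumed risks of 2% and 5%.

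**Does Kaplan-Meier remove the shortfall?** Simulation at an assumed 5% six-month risk (3,000 runs, 50 or 100 patients, constant-hazard and 80% patterns) says yes. At the final analysis the estimate averages 4.9% to 5.05%. At the interim it averages 4.2% to 4.3% under constant hazard and 4.8% under the 80% pattern, against true 5-month risks of 4.2% and 4.8%.

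**The case against.** **The protocol's Kaplan-Meier analysis is optional.** A reader might infer that the SAP breaks a protocol commitment. It does not: Protocol 6.7 says such plots may be produced, depending on the incidence of events, and its base summary is the percentage that the SAP specifies. This objection stands. What remains is that the SAP settled the option for every other listed endpoint and left this one out without a reason.

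**The final-analysis bias is below sampling error.** This also stands. With an assumed 50 CEA patients and 5 events, the exact 95% interval is 3.3% to 21.8%, while the shortfall is 0.2 to 0.5 percentage points. A reader might infer that the final rate is seriously biased; at 10% early termination it is not.

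**Six-month risk is the wrong yardstick at the interim.** A reader might set 4.3% or 6.1% against the 10% six-month risk and claim a shortfall of 57% or 39%. No estimator recovers risk beyond observed follow-up, so the comparison should be with the 5-month risk, as in the table.

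**The plan contains mitigations.** Adverse events are split at 30 days and shown by indication (SAP 2.17), discontinuations are tabulated with reasons (SAP 2.3), and patients asking to stop are encouraged to complete visits (Protocol 8). These help at the final analysis. At the interim, SAP 2.19 plans no sub-analyses by indication or event timing, so the first is lost where it is most needed.

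**The study is descriptive.** There is no performance goal, test or stopping threshold for this rate, and the interim omits Kaplan-Meier for every endpoint. Both points are correct and limit the consequence. They do not remove the risk of misreading an interim percentage that informs decisions about the study.

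**Conclusion.** The point holds in a limited form. The CEA primary endpoint has no analysis that accounts for length of follow-up, unlike every other endpoint on the protocol's Kaplan-Meier list. At the final analysis this is mainly a matter of consistency: a relative understatement of about 2% to 5% at the planned 10% early termination, and at most 10%. At the interim it is material: 4.3% against 8.4%, or 6.1% against 9.0%, narrowing to 7.8% against 9.6% if 80% of the risk falls in month 1.

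The direction rests on non-informative loss. The sizes rest on an assumed 10% risk, assumed event timing and uniform interim follow-up, so they illustrate scale and do not predict the result. If loss depends on risk, the error could be larger or smaller, and Kaplan-Meier would not correct it. The documents support neither a breach of the protocol nor a serious bias in the final rate.

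**What to change.** **SAP 2.10.** Add the cumulative incidence of the composite among CEA patients at 30 days and at 6 months, with 95% confidence intervals and numbers at risk, censoring at last contact. Read the six-month value at day 166 (180 days less the 14-day window), so that patients whose final visit falls early in the window are still at risk. Use Kaplan-Meier, or treat death without an event as a competing event; censoring deaths in Kaplan-Meier slightly overstates the risk. Keep the crude table beside it.

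**SAP 2.19.** Changing 2.10 alone leaves the interim untouched. For CEA patients, report the 30-day cumulative incidence and events per patient-month, with the distribution of follow-up, as a stated exception to the exclusions in that section. Give no six-month value: with at most 5 months of follow-up (about day 152), day 166 cannot be reached. State that crude interim percentages are not six-month risks. Events per patient-month average over early and late risk, so they need the follow-up distribution beside them.

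**Cost.** SAP wording and a little more analysis. Surgery, adverse event start, visit and discontinuation dates are already on the eCRFs in Protocol Appendix D, so no new data or visits are needed. The reported rate will be slightly less favourable.
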